Aim 2: To conduct an RCT comparing efficacy of TEAM vs. enhanced treatment as usual (ETAU) in 246 Ugandans (TEAM, N= 123; ETAU, N= 123) at high risk for stroke. Phase 2 consists of an RCT using a Type 1 hybrid effectiveness-implementation design, which rigorously tests the clinical intervention and secondarily gathers data to inform subsequent implementation efforts and research. The RCT will evaluate key primary (systolic BP) and secondary (biological and behavioral) outcomes indicative of stroke risk. H1: Individuals in TEAM will have significantly reduced systolic BP compared to individuals randomized to ETAU. H2: Individuals randomized to TEAM will have greater reductions in serum cholesterol compared to ETAU. H3: Individuals with diabetes randomized to TEAM will have improved glycemic control as measured by serum HbA1c compared to ETAU. Secondary outcomes also include other biomarker variables, stroke knowledge and attitudes, medication adherence and health resource use. We will also explore associations of age, gender, urban vs. rural residential status and stroke history (prior vs. no previous stroke) on TEAM outcomes.

Aim 3: Identify barriers and facilitators to TEAM implementation in order to inform subsequent scale-up and spread using qualitative methods and guided by an implementation conceptual model. As with Aim 1, Aim 3 evaluation will be guided by an i-PARIHS framework. Finally, the project will grow research capacity in stroke risk reduction, training the next generation of brain health investigators in SSA. The project will help establish a sustainable infrastructure that will facilitate future scale-up of TEAM in Uganda. Taken together, the proposed project has substantial public health importance and will provide the prerequisite data and infrastructure needed to help with reducing stroke burden in Uganda and other LMIC countries across the globe.

Study Design

The proposed project is a prospective, randomized effectiveness-implementation trial of TargEted MAnageMent Intervention (TEAM. N= 123) vs enhanced treatment as usual (ETAU, N=123) in Ugandans who are at risk for stroke or have had a stroke within the last 5 years.

Study Procedures

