In Phase 1 of the project, stakeholder's advisory board (SAB) will be convened across 3 Ugandan sites. The SAB will be composed of up to 15 relevant stakeholders including 3 stroke survivors, 3 individuals with multiple stroke risk factors as defined above, 3 family members, 3 clinicians and 3 administrators who practice in the proposed study enrollment sites. The purpose of the SAB is to refine the TEAM intervention content to meet the needs of patients and professional healthcare stakeholders and suggest how TEAM might best be incorporated into clinical workflow, as well as give guidance and feedback on recruitment methods and advertisements.

Phase 2 of the project will be conducted across 3 Ugandan sites that will enroll a representative sample of Ugandans at risk for stroke (Mulago, Nsamba and Mbarara Hospitals and their associated outpatient clinics). In the RCT portion of the study, 246 participants will be randomized at baseline on a 1:1 basis to receive either TEAM (N= 123) or ETAU (N=123) and will be followed for a total of 6 months. Since stroke is a moderately long-term health outcome (years to decades) that typically occurs in the presence of one or more stroke risk factors, the project will focus on testing whether TEAM can modify well-established short-term biomarkers that predict stroke risk, specifically BP control, serum cholesterol and blood glucose control. Secondary outcomes of interest include additional stroke risk biomarkers, (HDL, LDL, triglycerides) diet, exercise, use of alcohol and tobacco, stroke knowledge/attitudes, stress, and treatment adherence with risk-reducing medications. We will also explore associations of age, gender, urban vs. rural residential status and stroke history (prior vs. no previous stroke) on TEAM outcomes. To help inform future scale-up should RCT findings be positive, we will assess barriers and facilitators to TEAM implementation using both qualitative and quantitative methods.

Participants: Individuals will be referred by clinical providers at the sites and by self-referral in response to IRB-approved advertisements posted at the clinic site and in the local community. We also expect that some individuals might also self-refer by word of mouth after hearing about the project from someone they know.

Inclusion and Exclusion Criteria

	Inclusion Criteria for RCT participant
1.	Age range: ≥ 18 years

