Measures: Demographic variables and existing medical burden (assessed with the self-reported Charlson Index⁷⁹) will be evaluated at baseline, prior to study randomization. Baseline medical status will also be evaluated with personal and family stroke history as well as currently prescribed medications. Primary outcome of the RCT will be change in systolic BP from baseline to 6-month follow-up. Additional outcomes of interest will include diastolic BP, cholesterol/lipids and glycosylated hemoglobin (HbA1c) (approximately 5mL of blood is drawn per blood draw), body mass index (BMI), measures that evaluate diet, activity levels, substance use, self-efficacy, stroke knowledge, stress, medication adherence, medication access and health resource use. Quantitative measures will be repeated at 13-week and 24-week (6-month) follow-up except for laboratory testing, which will be conducted only at baseline and 24-week follow-up. Qualitative evaluation will be conducted at baseline and at 13-week follow-up.

[figure not shown]
Primary outcome: The primary study outcome is systolic BP measured at baseline, 13-week, 24-week (6 month). All BP measurements will adhere to a standardized procedure previously used by this study team.³⁰ Prior to BP measurement study participants will be requested beforehand to refrain from smoking and drinking alcohol or caffeinated beverages at least half an hour before the examination. BP will measured with an Omron automated sphygmomanometer model HEM 907 whose accuracy has been validated.⁸⁰ The participant will be asked to sit on a chair and rest quietly for 15 minutes with his/her legs uncrossed. The left arm will then be placed on a table with the palm facing upward and the ante-cubital fossa at the level of the lower sternum. Two arm cuffs that fitted arm circumferences 9-13 inches and 13-17 inches will be available for use in BP measurement. Three measurements will be taken at least 5 minutes apart. The average of the last two readings will be considered as the final blood pressure reading.

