Feasibility and Fidelity: Attendance for each TEAM and ETAU contact will be recorded. Acceptability for each intervention will be assessed at 13 weeks with a brief self-rated survey. Following Fraser et al.,⁷⁸ fidelity to the TEAM intervention will be assessed quantitatively and qualitatively. Fidelity to TEAM processes, content and format will be evaluated by random attendance of 20% of sessions by non-interventionist study staff to determine if sessions covered relevant TEAM constructs and health practices as identified in the specific sessions as well as assessment of if written prompts were appropriately utilized, and if sufficient time was devoted to the question/answer/ comment session. Each fidelity dimension will be rated on a 1-10 scale using the same evaluation process as in the TEAM pilot.

Risks to Research Participants

Patients will not be compelled to participate in any way in the activities of the project. Participants will be free to withdraw from the project at any time without penalty. This study involves participating in surveys and completing a set of self-report instruments, along with qualitative interviews. All instruments have been utilized in outpatient research settings and are not associated with risks to patients.

The behavioral intervention intended to enhance self-management is not expected to increase risk to individuals. Because of the nature of group interaction, patient confidentiality cannot be guaranteed. However, the importance of respecting other group members' privacy will be stressed to all participants.

The risks to the participants will be primarily those of talking about some matters that they may find uncomfortable. All participants will have blood drawn twice, at baseline and at 6-month follow-up. There is minimal risk to blood draw. However, when a blood sample is taken, participants may experience temporary discomfort, bruising, and/or infection or blockage of the vein where the needle is put into their arm. On rare occasions, fainting may occur.

PEDs are not expected to incur risk, however in the unlikely event that participation in TEAM is experienced as stressful, appropriate measures will be taken by the on-site clinical members of the study to minimize burden or distress.

Potential Benefit to Research Participants

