Quantitative data Analysis: Preliminary descriptive analyses will examine change over time in systolic BP as well as secondary outcomes. The measures of interest are valid and reliable, and have been used in stroke studies in the SSA setting.^{24, 30, 88, 97, 98} Primary and secondary outcome measurements will be assessed at baseline prior to randomization to either TEAM or ETAU, and at the 13 week and 6 month time-points using the same methods as in our pilot work. Of primary interest is the treatment by time interaction in systolic BP, measured from baseline to 6 months after randomization between TEAM and ETAU. Explanatory variables will include age, gender, stroke history and rural vs. urban status.

The 13-week systolic BP measurement will reflect the period following baseline (when individuals participating in TEAM Uganda will have just completed the “intensive” group sessions), and it will be used to assess for within-subject differences from baseline to 13 weeks and 13 week to 6-month time periods. This will allow for a greater understanding of the time course for when the expected reductions occur in the TEAM Uganda group, which we expect to mostly occur after the “intensive” group sessions have ended. We will analyze change from baseline to 13 weeks as well, analyzing contrasts within the mixed model framework.

For aim 2, we will use 2 group by 3 time waves repeated measures analysis of variance (RMANOVA) for each of the 3 hypotheses in Aims 2. These analyses will compare two groups (TEAM intervention vs. enhanced treatment as usual (ETAU)) across three time waves of systolic BP (H1), serum cholesterol (H2), and serum HbA1c (H3). When using a repeated measures ANOVA, it not only assesses mean differences across time, but also assesses group differences, as well as, the interaction of time X group which will allow us to test the trend of the means over time across the three groups. The repeated measures ANOVA, not only can be used to determine if there are mean differences across the three time periods, it can also utilize orthogonal polynomial contrasts to determine linear and quadratic trends of the means across time. Orthogonal polynomials are weights

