assigned to each time period that model a linear or quadratic (non-linear) trend. Repeated measures ANOVA can determine if these trends in the means are significant. A linear trend is indicated if there is a steady increase or decline in scores from the first time wave to the third time wave. A quadratic trend is indicated if there is a change in direction based on scores across the time waves. For example, if there is a decrease in mean scores from T1 (baseline) to T2 (13 weeks), but an increase in scores at the T3 (6 months), this would be indicative of a U trend for the three time periods and a return toward the mean score from T1 to T3. A quadratic trend can also indicate a single change in direction in the trend of the means, for example, if there is a decline in means scores from T1 to T2, and the decreased mean score is maintained at T3. The major assumption to be tested with repeated measures ANOVA is sphericity. Sphericity is a form of compound symmetry and refers to the equality of variances of the differences between each time wave.⁹⁹ If the assumption of sphericity is violated based on the Mauchly's test, SPSS provides an adjusted F, df, and p-value in repeated measures ANOVA to account for this violation. We may also explore repeated measures mixed model approaches to analyze change from baseline to 13 weeks as well, analyzing contrasts within the mixed model framework.

Secondary outcomes: We will model secondary outcomes over time in a similar manner. We will consider generalized linear models when distributions of outcomes are not approximately normally distributed, or transformations of outcome variables to normality. We will also conduct exploratory moderator analyses of the explanatory variables in the primary mixed model. Mediation analyses also will be explored. Potential mediators include dose of TEAM session exposure, medication prescription/access and adherence to a heart healthy diet. Variables with (change) values that appear to be associated with change in systolic BP levels and that appear to differ by treatment will be considered further as mediator variables, following as in MacKinnon (2008)¹⁰⁰ and Preacher and Hayes (2008).¹⁰¹ This will involve single mediator analyses as well as multiple mediator models. These analyses will involve the treatment variable and change in systolic BP values. Associated standard errors of estimated indirect effects will be derived through bootstrapping, using the M-Plus software.

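### Cholesterol (H2) and HbA1c (H3) are assigned a three-wave repeated-measures ANOVA, but blood is drawn at only two visits, so the written test cannot be run

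*Combined protocol and SAP*

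**What the plan says.** The Quantitative data Analysis section assigns one method, a two-group by three-wave repeated-measures ANOVA, to each Aim 2 hypothesis. It names the outcomes: "across three time waves of systolic BP (H1), serum cholesterol (H2), and serum HbA1c (H3"). It then describes linear and quadratic polynomial contrasts over baseline, 13 weeks and 6 months, and adds: "The major assumption to be tested with repeated measures ANOVA is sphericity".

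Two other sections set the blood sampling. The Measures section repeats the quantitative measures at 13 and 24 weeks "except for laboratory testing, which will be conducted only at baseline and 24-week follow-up". Risks to Research Participants states: "All participants will have blood drawn twice, at baseline and at 6-month follow-up".

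The analysis section also has a general sentence without the laboratory exception: "Primary and secondary outcome measurements will be assessed at baseline prior to randomization to either TEAM or ETAU, and at the 13 week" and 6-month visits. Its Secondary outcomes paragraph says "We will model secondary outcomes over time in a similar manner". Study Procedures lists among the secondary outcomes "additional stroke risk biomarkers, (HDL, LDL, triglycerides"). Under Aim 2, H3 is confined to a subgroup: "Individuals with diabetes randomized to TEAM will have improved glycemic control as measured by serum HbA1c compared to ETAU".

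**The concern.** For two of the three named Aim 2 hypotheses, the written model needs a measurement that the schedule does not collect. The 13-week laboratory value is absent by design for everyone, so the Missing Data section, which deals with values lost despite retention efforts, does not help. A complete-case three-wave ANOVA would have no eligible participants. A mixed model with visit as a factor would have nothing from which to estimate the 13-week means.

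Whoever runs the analysis will therefore have to replace the written test. At least two valid replacements exist: a comparison of change scores, and a comparison of 6-month values adjusted for baseline. They can give different estimates and p-values on the same data. If the choice is left open until the data are seen by arm, the tests of H2 and H3 are not fully pre-specified.

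**Working it through.** **The plan's own figure.** The only power figure is for systolic BP (Sample size calculations): power 0.80 for 10 mm Hg, N = 246, SD 25.84, within-subject correlation 0.57, 25% attrition, two-sided 0.05.

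- SD of change = 25.84 × √(2 × (1 − 0.57)) = 23.96.
- Completers per arm = 123 × 0.75 = 92.25, taken as 92.
- Two-sample power = 0.808. In reverse, 91 evaluable per arm gives 122 per arm after attrition (91/0.75), or 244 in total.

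The stated 0.80 is reproduced. Systolic BP is measured at all three visits, so this figure is not touched. No corresponding figure is given for H2 or H3.

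**What two draws do to the written test.** Inputs: 246 × 0.75 = 184.5, taken as 184 completers; 2 groups; w waves. Formulas for an unadjusted complete-case ANOVA:

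- group-by-time df = (2 − 1)(w − 1)
- error df = (184 − 2)(w − 1)
- Mauchly df = w(w − 1)/2 − 1

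| | w = 3 (as written) | w = 2 (as collected) |
|---|---|---|
| Group-by-time df | 2 | 1 |
| Error df | 364 | 182 |
| Mauchly df | 2 | 0 |
| Rank of the basis 1, t, t² | 3 | 2 |

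With rank 2 there is no quadratic contrast. With 0 df there is no sphericity test; sphericity holds trivially. For H3 the numerator df is likewise 1, but the error df depends on the number of participants with diabetes, which the documents do not give.

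**What remains testable.** With two waves, the group-by-time F is the square of the two-sample t on change from baseline. On simulated data with 92 per arm both equalled 12.80. Dropping the missing wave therefore gives a valid change-score test.

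**Why the choice of two-visit test matters.** Let ρ be the baseline-to-6-month correlation and k the baseline SD divided by the 6-month SD. In large samples the variance of the baseline-adjusted (ANCOVA) estimate relative to the change-score estimate is (1 − ρ²)/(1 + k² − 2ρk). The documents give neither quantity for laboratory outcomes, so the values below are assumptions.

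| k | ρ = 0.5 | ρ = 0.7 |
|---|---|---|
| 0.85 | 0.860 | 0.958 |
| 1.00 | 0.750 | 0.850 |
| 1.15 | 0.640 | 0.716 |

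At k = 1 the ratio simplifies to (1 + ρ)/2, a variance 15% to 25% lower with ANCOVA. Over the whole grid the reduction runs from about 4% to 36%. These figures bear on which replacement to choose; they do not measure the error in the plan.

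**The case against.** The strongest reply is that the consequence is small. Cholesterol and HbA1c are secondary outcomes. Repeated-measures ANOVA reduces naturally to a 2 × 2 interaction when only two visits exist, and that test is valid. The polynomial contrasts are described as something the method can do, and the sphericity correction applies only if the assumption fails, so nothing invalid would result. Only cholesterol and HbA1c are expressly given three waves; the extension to HDL, LDL and triglycerides is by inference. ANCOVA is a preference, its gain rests on assumed correlations and SDs, and the large-sample argument is weaker for H3, whose subgroup size is unknown. The degrees of freedom assume complete cases and no covariates, whereas the plan also mentions explanatory variables and mixed models.

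Much of this stands as a limit on weight. The outcomes are secondary, the default reduction is valid, the degrees of freedom are illustrative, and an equivalent two-visit mixed model would serve as well as ANCOVA. It does not remove the contradiction. Three waves are expressly assigned to two laboratory outcomes, two separate sections allow only two draws, and no two-visit test is written anywhere. The general sentence about 13-week assessment cannot be read as scheduling a third draw, because it conflicts with both of those sections. The laboratory rows of Table 1 are not legible in the available text and cannot settle the matter. The optional mixed model is proposed for change from baseline to 13 weeks, an interval with no laboratory result.

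**Conclusion.** The concern holds. As written, the H2 and H3 analyses cannot be carried out on the scheduled data: the interaction has 1 degree of freedom instead of 2, no quadratic trend can be estimated, and Mauchly's test has 0 degrees of freedom. Two outcomes are affected expressly, and HDL, LDL and triglycerides are affected if modelled in the same way, making five in all. This rests on the two-draw schedule given in the Measures and Risks sections; the error degrees of freedom rest also on 184 complete cases without covariates.

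The primary outcome, its model and its power are untouched, and H2 and H3 can still be tested validly. It is a specification error in secondary analyses that should be fixed, not a threat to the trial's main result.

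**What to change.** 1. Reconcile the Measures and Risks sections with the Data Analysis Plan on the number of laboratory time points.
2. If the two-draw schedule stands, state that H2 and H3 are tested by ANCOVA, or an equivalent two-visit mixed model, of the 6-month value on arm, adjusted for baseline value, site and the randomisation factors. Those factors are diabetes and previous stroke for H2. For H3, analysed in participants with diabetes at baseline, only previous stroke remains.
3. Restrict the three-wave, polynomial and sphericity text to outcomes measured at three visits, and give HDL, LDL and triglycerides the same two-visit analysis.
4. Add the laboratory exception to the general sentence on 13-week assessment.

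This should be fixed before any unblinded analysis. The DSMB section plans an interim analysis once half the participants have completed 6 months, and the documents do not say whether it has taken place. If laboratory outcomes have already been examined by arm, the amendment should say so.

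The cost is SAP wording only, provided the two-draw schedule stands; the adjustment uses variables already collected.

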TEAM: Similar to previous self-management approaches developed by these investigators^{16, 31, 33} TEAM is informed by principles of social cognitive theory.⁷⁶ TEAM uses nurses and peer educator dyads (PEDs) composed of patients and their care partners to co-deliver an intervention intended to help reduce future stroke risk (Figure 1). Team begins with one 60-minute 1:1 orientation session, in which the nurse and PED meet with the patient and his/her care partner. This is followed by 6 hour-long group sessions with 6-8 patients and their care partners held approximately weekly. The first orientation session will be done approximately 1 week post baseline, followed by group sessions were done at 2, 4, 6, 8, 10 and 12 weeks post-baseline. Our pilot work suggests that the timing and format of the groups is highly acceptable to participants, with robust attendance/retention. Individuals who miss a group session are encourage to complete a make-up session conducted immediately before or after regularly scheduled groups. In cases where logistic barriers prevent in-person attendance, participants may conduct make-up sessions by phone with the nurse educator. To reinforce learning after the TEAM group sessions are done, 3 brief (approximately 10-20 minute) monthly telephone calls occur between the nurse and the patient over the next 3 months. These calls support ongoing self-management and facilitate linkage with other care providers. All TEAM participants continue in treatment with their regular medical care providers and TEAM visits will take place in these clinics.

Figure 1: TEAM participants and interactions

*Patient care partner also encouraged to participate if available

TEAM Curriculum: Topic content is noted below. In the RCT, content is delivered in 6 sessions.

Session 1: Orientation and introductions, Emphasize ground rules, Establish a therapeutic relationship, Discuss facts and myths about stroke, Overview and interactive discussion of stroke risk factors

Session 2: Medications to manage complications and reduce future risk, Nutrition for best physical and emotional health, Healthy cooking and use of salt in food preparation

Session 3: Problem-solving skills and the IDEA approach (Identify the problem, Define possible solutions, Evaluate the solutions, Act on the best solution), Effects of exercise, smoking and other substances in recovery

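### TEAM session dose is listed as a mediator although it is zero by design in ETAU, so its indirect effect is open to confounding and too imprecise to use; same-data screening inflates the other indirect effects that survive

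*Combined protocol and SAP*

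**What the plan says.** The Secondary outcomes paragraph of the Data Analysis Plan opens the topic with "Mediation analyses also will be explored". It names three candidates. The first is session dose: "Potential mediators include dose of TEAM session exposure". The other two are prescription of or access to medication, and keeping to a heart-healthy diet. Candidates are then chosen from the trial data: those whose changes look related to the fall or rise in systolic BP, and "that appear to differ by treatment will be considered further as mediator variables". On what follows, the paragraph says "This will involve single mediator analyses as well as multiple mediator models", and on inference, "Associated standard errors of estimated indirect effects will be derived through bootstrapping, using the M-Plus software".

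It gives no threshold for the screen and does not say whether the association with blood pressure is judged within arm or overall. It sets out no time order, no confounder set and no sensitivity analysis for mediation.

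The TEAM paragraph describes a 1:1 orientation session, and then: "This is followed by 6 hour-long group sessions with 6-8 patients and their care partners held approximately weekly". Three monthly nurse calls come afterwards. The ETAU paragraph gives that arm one orientation visit and nine calls, delivered by different nurses. The Feasibility and Fidelity paragraph records contacts in both arms, but the mediator named is exposure to TEAM sessions, not total contacts. The documents do not state how dose is coded in ETAU; zero follows from the design.

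**The concern.** A mediation estimate multiplies two paths: treatment to mediator, and mediator to outcome given treatment. For session dose the first path is simply mean attendance in TEAM, so it says nothing about mechanism. Because dose is constant in ETAU, the second path is estimated only by comparing TEAM participants who attended more with those who attended less, and randomisation does not protect that comparison. The matching direct effect is an extrapolation to TEAM participants who attended no sessions.

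The other two candidates can vary in both arms, so they do not share this problem. They do go through a screen on the same two paths that define the indirect effect, in the same data, with no allowance for selection.

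At stake is the trial's account of how TEAM works. It could attribute a large blood pressure effect to attendance when none exists, or report the remaining mediators as stronger than they are.

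**Working it through.** **Design inputs (Sample size calculations).** The SD is 25.84, within-subject correlation 0.57, 123 per arm and attrition 25%.
- SD of change = 25.84 × √(2 × (1 − 0.57)) = 23.96, taken as 24 mmHg.
- Completers per arm = 123 × 0.75 = 92.25, taken as 92.
- Check on the plan's own figure: 10 / (23.96 × √(2/92)) = 2.83, which gives power of about 0.81. This reproduces the stated 0.80. No power figure is given for mediation.

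**Assumed, not in the documents.** Mean attendance is 5 of 6 group sessions with SD 1.5. The within-TEAM correlation r between attendance and blood pressure improvement is 0.1, 0.2 or 0.3, arising only from shared causes. The true treatment effect is zero.

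**Dose, by formula.**
- Treatment-to-dose path: a = 5.
- Dose-to-BP path: b = −r × 24 / 1.5. At r = 0.1 this is −1.6 mmHg per session.
- Indirect effect a × b: −8, −16 and −24 mmHg at r = 0.1, 0.2 and 0.3. The direct effects are +8, +16 and +24, because the total is zero.
- Approximate standard error of a × b: 5 × 24 / (1.5 × √92) = 8.3 mmHg. Simulation gives 8.5, so the 95% half-width is 1.96 × 8.5 = 17 mmHg.
- Collinearity with treatment: total variance of dose = 25/4 + 2.25/2 = 7.375, of which 1.125 lies within arm. The variance inflation factor is 7.375 / 1.125 = 6.6.

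**Dose, by simulation (92 per arm, zero treatment effect).**

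| Within-TEAM r | Indirect effect, mmHg | Significant, before the screen | Significant and marginal BP association p<0.05 |
|---|---|---|---|
| 0.1 | about −8 | 15% | 2% |
| 0.2 | about −16 | 49% | 8% |
| 0.3 | about −24 | 83% | 19% |

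With no confounding the error rate is about 5%.

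The last column is low because, with no treatment effect, the ETAU zeros dilute the overall correlation. It equals r × 0.5 × 1.5 / √7.375, or 0.028, 0.055 and 0.083. If the association is judged conditional on treatment, the middle column applies. The plan does not say which is meant.

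**Sensitivity to the attendance model.** Rounding attendance and capping it at 6 sessions gives −9, −17 and −26 mmHg, significant in 15%, 43% and 78%. A separate simulation restricted dose to 0–6 sessions at 70% or 80% mean attendance. At within-TEAM correlations of about −0.11, −0.16 and −0.24 (more sessions, larger fall in BP), false positives before the association screen were 19–22%, 33–37% and 64–70%. Without confounding they were 5–7%.

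**The other mediators (92 per arm, screen at an assumed p<0.05 on both paths).**
- True indirect effect zero: the overall false-positive rate per variable is 0.1–5.1% across screening thresholds from p<0.05 to p<0.20. Screening can only remove rejections.
- True indirect effect 0.06 SD: the estimates that survive average about 0.115, and 0.115 / 0.06 = 1.9 times.
- True 0.045 in size: survivors average 0.076, or 68% too large.
- True 0.120 in size: survivors average 0.137, or about 15% too large.

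**The case against.** The strongest reply is that this is exploratory. The candidates are only potential mediators, and H1 to H3, the sample size and the primary test do not depend on them. That stands, and it limits the weight of the point.

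Four stronger readings are tempting, and the documents do not support them.

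- A reader might infer that the mediation results will be spurious. They need not be. The bias in dose requires attendance and blood pressure change to share causes; otherwise the error rate is about nominal. Such sharing is plausible, since the plan itself expects missed sessions and logistic barriers, but its strength is assumed here. The structural zero does not reach medication prescription/access or diet.
- A reader might infer that dose always passes the screen. Only one of the two conditions is automatic. With a marginal p<0.05 association and no treatment effect, dose passes in about 7%, 12% and 21% of trials at r of 0.1, 0.2 and 0.3. The protection is fragile, however. In the 0–6 session simulation with a true 10 mmHg effect not acting through dose, the association passes in roughly 70–95% of trials. Dose is then passed and falsely significant in 18–20%, 32–36% and 62–65% at the three confounding levels.
- A reader might infer that screening manufactures false mediators. Among null variables that pass, most can look significant, but few pass, so the overall rate per variable stays at or below about 5%. What screening damages is the size of the surviving estimates.
- A reader might infer that these results drive scale-up. Aim 3 relies on qualitative methods and an implementation framework, and no section feeds mediation results into it.

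The lack of a stated time order does not affect dose either: sessions end at week 12, before the 6-month reading.

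**Conclusion.** The point holds as a modest one about an exploratory analysis. Session dose is unsuitable as a mediator here. With confounded attendance it can yield a spurious indirect effect of about −8 to −24 mmHg, against a design difference of 10. Without confounding, an interval of about ±17 mmHg tells the reader little. The false-positive rates (15–83% before the screen, 2–19% with a marginal screen) depend on assumed attendance, assumed confounding, a zero treatment effect and an unstated screening rule, so they are illustrations rather than forecasts. For the other two mediators the defect is inflation of surviving estimates, from about 15% to about 1.9 times depending on the true effect and threshold, with no rise in the per-variable error rate. The primary and secondary hypotheses are unaffected.

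**What to change.** Amend the Secondary outcomes paragraph as follows.

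1. Remove session dose from the mediator list and report it descriptively as exposure or adherence in TEAM. An estimate using randomisation as the instrument for sessions attended is optional and exploratory. It is a rescaled intention-to-treat effect and says nothing about mechanism. The TEAM follow-up calls and the ETAU contacts strain its assumption that allocation acts only through sessions, and the text should say so.
2. Drop the screen on apparent associations. Report medication prescription/access and heart-healthy diet whatever the result.
3. Fix the time order: mediator change from baseline to 13 weeks, outcome 6-month systolic BP adjusted for baseline systolic BP.
4. Adjust for baseline covariates already collected, and add a sensitivity analysis for unmeasured mediator–outcome confounding, which remains for these two variables as well.
5. Label all mediation results exploratory.

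The cost is a few sentences and slightly more analysis. The Measures section already repeats the quantitative measures at 13 weeks, though it is worth confirming that this covers prescribed medications, which that section also lists at baseline. Attendance is already recorded, and sample size and power do not change. The downside is that mediator change after week 13 is not captured.
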